 - Enrolled in opioid substitution program (e.g. methadone or suboxone) and receiving doses.

Inclusion for heroin users:

- 2) Use of heroin through any route of administration at least 2 times in the last 30 days (or if institutionalized recently, in the most recent month they were not institutionalized) with or without other risks being present.

Inclusion for prescription-type opioid users:

- 3) Use of pharmaceutical opioids at least 2 times in the last 30 days (or if institutionalized recently, in the most recent month they were not institutionalized) with other risks being present.

Inclusion for opiate registry users:

- 4) Average daily dose of prescribed opioids consumed is 30 mg morphine equivalent analgesic dose or higher without other risks being present.

In the case of known pregnancy, subjects will not be excluded and will be offered naloxone if randomized to the intervention arm.

Exclusion criteria

- 1) Unwilling to allow further access to medical or drug treatment records.
- 2) Inability to communicate in English.
- 3) Current active suicidal ideation.
- 4) Significant cognitive or psychiatric impairment (per judgment of clinical staff)
- 5) Inability to provide adequate contact information to assist with follow-up.
- 6) Under age 18 or over age 70 at time of recruitment.
- 7) Not currently living in Washington State or planning to move from Washington State within the following year.

8) Receiving treatment for sexual assault.

9) Have non-expired take-home naloxone at home, on their person, or in their possessions.

Participation in the study is not appropriate for subjects under care for terminal illness, as known reduced life expectancy may skew study results, and the use of high doses of opioid medications may be used during end of life care.

Potential Subjects Identified

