Some subject will be identified through prescreening of intake records and medical history for patients admitted to hospital, including those admitted for overdose, or in transit to the ER for overdose. In the emergency departments several large monitors display information related to admission. Some subjects initially seen in the ER will be admitted to the main hospital, but will be listed in ER medical records for the past 3 days. Some subjects may bypass emergency services and be admitted directly into inpatient care. Medical records would again be screened for eligibility. Finally some patients will be recruited through flyers and word of mouth without the use of medical records screening.

We will use this information in combination with information available from prescreening medical records to identify potential subjects. We will communicate with clinical staff pointing out potential subjects identified in prescreening, and reminding clinical staff of potential subjects to be aware of for inclusion. Study staff will regularly attend staff meetings to educate them about the study, enlist their help in identifying potential subjects and obtain feedback on recruitment protocols.

Clinical staff will be asked to look for patients who have experienced overdose, exhibit physical symptoms of drug use (such as abscesses or track marks), present for care with symptoms of pain without apparent injury, or exhibit signs of overmedication (such as pinpoint pupils) for admissions unrelated to drug use or overdose. Clinical staff will also be asked to look for subjects who use opioid medications, have a high number of prescriptions or prescribers for controlled substances (such as opioids or benzodiazepines), or high emergency room utilization or admissions.

If a potential subject is appropriate and medically stable clinical staff may either inform the subject of the availability of the study or confirm that research staff may make the initial approach with subjects. A study flyer will also be made available to clinical staff. If patients express interest, we will approach the potential subject.

Subject Approach and Consent for Screening

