In order to determine whether there is recruitment reactivity, whether those enrolled in either arm of the study have a change in behaviors compared to those not enrolled, we will examine ED re-visit rates at two years for those receiving standard care compared to those with similar demographic characteristics, CPT codes and ED visit dates, but were not enrolled. While this will not directly measure the impact of recruitment on overdose, it will provide some information about recruitment reactivity. Subsequent to intent to treat analyses we will examine whether any subjects in the standard care group received take-home naloxone and overdose prevention and intervention training i.e. “crossed over”. If so, it is possible that this intermediate group might be more similar to the intervention than the standard care group. Crossovers will be identified by an interview question, such as “Did you possess or have ready access to naloxone during the past 3/6 months?” If there is a group that crossed over, post-hoc analyses will compare overdose rates at two years for the cross over group compared to each of the other two study arms. Completion level of administrative data will be assessed by the interview questions at each follow up that document what types of services, in broad categories, were

obtained at non-HMC or non-UWMC facilities or ambulance services not in Seattle-King County. This will allow for an evaluation of *ascertainment bias*, that is, how complete data based on HMC/UWMC and King County ambulance data are and whether there are differential levels of data completion by study arm assignment.

Missing data and dropouts

Missing data will be minimized by the study procedures described above. However, missing data are inevitable and could lead to biased results. Baseline data values and study arm assignment will be examined to determine the relationship with missingness. Sensitivity analyses will be conducted that assume any person lost to follow up had constant levels of drug use based upon their most recent measurement point. This will provide some guidance as to the amount of bias possibly introduced by missing data.

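### The recruitment-reactivity check compares ED re-visit levels without matching on opioid use or prior ED use, so it can show a difference without reactivity or hide a real one

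*Combined protocol and SAP*

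**What the plan says.** In the combined protocol and SAP, *Other analyses*, the purpose of the check is to learn "whether those enrolled in either arm of the study have a change in behaviors compared to those not enrolled". The method rests on "ED re-visit rates at two years for those receiving standard care compared to those with similar demographic characteristics, CPT codes and ED visit dates". The comparators are described as similar patients who had visits "but were not enrolled". The enrolled side is thus the standard-care arm alone, the outcome is a level after the index visit, and three matching factors are named. No model, test, pre-visit period or eligibility condition for the comparators is stated. One limitation is given: "While this will not directly measure the impact of recruitment on overdose, it will provide some information about recruitment reactivity".

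Other sections describe who gets into the trial:
- *Eligibility Criteria* rests on opioid use or opioid treatment. The heroin group, for example, requires "Use of heroin through any route of administration at least 2 times in the last 30 days".
- *Potential Subjects Identified* gives clinical staff a list of cues. They include use of opioid medication and signs of overmedication "for admissions unrelated to drug use or overdose", and the list ends with "or high emergency room utilization or admissions".
- The same section allows direct inpatient admissions, flyers and word of mouth, and *Study Design* names Evergreen Treatment Services as a site.
- *Exclusion criteria* includes "Not currently living in Washington State or planning to move from Washington State within the following year".

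**The concern.** The question is about change, but the analysis compares only later levels between groups that were not randomized. Such a comparison cannot separate an effect of enrollment from differences that were already there.

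The named matching factors leave out two things tied to enrollment. Opioid use defines who is eligible, yet nothing requires a comparator to be an opioid user. Heavy prior ED use is a recruitment cue and also the earlier value of the check's own outcome. Procedure codes may not stand in for opioid use, because staff are also asked to look for overmedicated patients admitted for other reasons.

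At stake is how the standard-care arm is read. If enrollment alone changed its behavior, the trial would be comparing the intervention with an altered control. This is the one analysis the plan gives to that question, and its result could be reported as evidence either way. By contrast, the cost model under *Planned analyses*, Aims 3 and 4, controls for pre-randomization costs, although randomization already protects that comparison from bias.

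**Working it through.** **1. The plan's own figures.** None is given for this check. The only design calculation in the plan, 219 per arm (*Sample Size Calculation*: 20% versus 10%, power 0.80, 0.05), reproduces exactly with a two-sided test and continuity correction; without the correction it is 199. It concerns overdose and does not bear on the check.

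**2. Entry factors set against the check.**

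| Factor | Role in entering the trial | Role in the check |
|---|---|---|
| Opioid use or treatment | Basis of eligibility | Not named; procedure codes may capture part |
| Prior ED use | One staff cue among several | Not named |
| Washington residence | Non-residents and planned movers excluded | Not named |
| Suicidal ideation, psychiatric or cognitive impairment, poor contact details | Excluded | Not named |
| ED visit date | Not required (flyer, inpatient, treatment clinic) | Matching factor |

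**3. Expected difference with no reactivity, reading the rate as a proportion re-visiting.** Let a high-use stratum re-visit with probability pH and other patients with pL, and let the stratum make up fE of the enrolled and fC of the comparators. Each group's proportion is p = f × pH + (1 − f) × pL, so the difference is (fE − fC) × (pH − pL). The chance of a significant result is Φ[(|d| − 1.96 × SE0) / SE1], where SE0 uses the pooled proportion and SE1 the two separate ones. The 500 standard-care subjects come from the plan (250 in each of two user types). The 500 comparators, the two-sided 0.05 test and all probabilities and shares are assumptions.

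| pH, pL | fE, fC | Proportions | Difference | Chance significant |
|---|---|---|---|---|
| 60%, 40% | 50%, 50% | 50% vs 50% | 0 | 5% |
| 60%, 40% | 50%, 40% | 50% vs 48% | 2 points | 9% |
| 60%, 40% | 50%, 30% | 50% vs 46% | 4 points | 24% |
| 50%, 40% | 100%, 50% | 50% vs 45% | 5 points | 35% |
| 60%, 40% | 100%, 50% | 60% vs 50% | 10 points | 89% |
| 60%, 40% | 100%, 20% | 60% vs 44% | 16 points | >99% |
| 60%, 40% | 40%, 50% | 48% vs 50% | −2 points | 9% |

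The last row shows that the sign depends on which group has more high users.

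**4. A real 20% reduction, reading the rate as visits per year.** Assume 6 visits a year for frequent users and 1 for others, so the mean is 6f + (1 − f) = 1 + 5f. With 10% frequent users among comparators, their mean is 1.5.
- 40% of the enrolled: mean 3.0, ratio 3.0/1.5 = 2.0 with no reactivity; 2.0 × 0.8 = 1.6 with the reduction.
- 20%: mean 2.0, ratio 1.33; × 0.8 = 1.07.
- 15%: mean 1.75, ratio 1.167; × 0.8 = 0.93.

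The reduction is hidden exactly when (1 + 5f) × 0.8 = 1.5, that is f = 17.5%. Above that share it looks like an increase; below it, a decrease still shows.

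**5. The same reduction on the proportion scale (60% and 40%).** With shares of 40% versus 10%, the proportions are 48% versus 42%, and 48% × 0.8 = 38.4%. With 20% versus 10%, they are 44% versus 42%, and 44% × 0.8 = 35.2%. Both remain below 42%, so the decrease is visible, though its size is distorted. The plan does not say which meaning of rate applies.

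**The case against.** A reader might infer that the check is bound to show a difference, or that a true fall in visits would be read as a rise. The documents do not support either reading. They give no re-visit rates, comparator mix or code list. If the codes and the loose requirement of similarity pick up opioid-related care well, the groups could be close. Sign reversal appears only in some assumed scenarios.

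Nor is prior ED use an entry criterion. It is one cue in a list with overdose, track marks, pain without apparent injury and multiple prescribers, and some subjects arrive without records screening. Selection also runs in more than one direction. Comparators who leave Washington may have visits that go unrecorded, which lowers their rate. Patients excluded for suicidal ideation, psychiatric impairment or poor contact details can remain among the comparators and might raise it.

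Matching on ED visit date arguably implies restriction to subjects who have an ED visit, and the documents do not say that flyer recruits lack one. Finally, the analysis is supportive, no decision rule rests on it, and the plan claims only that it is somewhat informative.

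All of this stands, and it limits the size of the point. It does not remove the confounding: neither factor is named for matching or adjustment, no before-to-after contrast is planned, and the one limitation given does not mention selection.

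**Conclusion.** The concern holds in a limited form. As written, the check cannot separate reactivity from selection. The spurious difference could be nil or large, and its direction cannot be determined from the documents. The figures above are illustrations on assumed rates and shares, not estimates for this trial.

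A reader might also infer that the trial's main results are compromised. They are not: both arms pass through the same recruitment, and the randomized comparisons do not use the unenrolled group. Only the inference about reactivity in the standard-care arm is at risk. The change is worth making because it is cheap, not because the trial depends on it.

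**What to change.** Amend *Other analyses* as follows:
- Limit the check to standard-care subjects with an index ED visit at HMC or UWMC.
- Choose comparators with opioid-related indicators in their visit records, within the study age range and with a Washington address. The documents describe no log of patients flagged at record prescreening, so the visit records are the safer source.
- Match on or adjust for the number of ED visits in the year before the index visit, or compare the before-to-after change in ED visit rate between groups. Choose one in advance and define the rate. If change is used, note that unequal prior use leaves it open to regression to the mean.
- Report that residual selection remains, because comparators include decliners and patients the trial would exclude.

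Cost: SAP wording and a further pull of comparators' prior ED visits, presumably from the records that supply their re-visits. The pre-randomization data for Aim 4 cover enrolled subjects only. There will be fewer comparators, and the check will not speak to subjects without an ED visit.

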*Past 3 months timeline for 3 and 6 month follow ups, past 6 months used at 12 month follow up.

Brief Behavioral Change Counseling (BBCC)

The BBCC will be conducted according to the demeanor and guidelines of Motivational Interviewing (MI), a style for counseling patients about sensitive behaviors and for giving them information to enhance their health and safety in a non-judgmental manner. MI has been widely implemented in brief intervention studies for drug use and other behavior change. MI is non-confrontational and respectful of subjects' autonomy to discuss or not discuss sensitive topics. The BBCC will consist of 4 elements:

- 1) The interventionist will show to the patient an approximately 8-minute video on overdose prevention, recognition and intervention, which subjects will view on a laptop while they are using headphones. The interventionist will debrief the video with subjects and answer questions.
- 2) Next, the interventionist will review with subjects their overdose risk. This task involves informing subjects of the “good news” about overdose risks they are NOT incurring in their current behaviors for the purpose of reinforcing and hopefully continuing more positive health behaviors (e.g., not inappropriately mixing other drugs or alcohol with

opiates). Next, the interventionist will respectfully and in a neutral tone review with subjects the behaviors that currently place them at risk for opiate overdose (e.g., using opiates when alone or after a long period of abstinence).

- 3) From the video and risk feedback, the interventionist will segue into an open discussion of any changes subjects are thinking of making to increase their safety from overdosing. If at any time during the interview, subjects indicate that they would prefer to quit opiates or to seek opiate detox or treatment, the interventionist will help with these referrals. The discussion will culminate in a summary of healthy changes, if any, that subjects intend to make. Subjects will take with them a handout that has been customized to summarize any changes subjects indicate that they want to make.

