abusers (no regular heroin use) indicates a rate approximately half that of heroin users based upon analyses conducted by [name] of interviews from 1,661 clients entering methadone maintenance treatment which indicate a *lifetime* overdose rate for pharmaceutical opioid abusers (25%) that is half the rate of heroin abusers (49%). These findings were extrapolated to a 50% lower rate of *annual* overdose, the validity of which cannot currently be determined, but will be ascertained at the conclusion of this proposed study. We are assuming an annual overdose rate of 10% for pharmaceutical opioid users, or 20% over two years which is the amount of time over which follow up via administrative data will be collected. The power estimates above therefore address one year overdose rates for heroin and 2 years for pharmaceutical opioid users.

Planned methodology

Intent to treat analyses will be the primary analytic approach used to analyze the data resulting from this randomized controlled study. Intent to treat analyses compare those assigned to the intervention group to those in the standard care group, regardless of whether those in the standard care group receive some amount of the intervention.

Planned analyses

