Aim 1 Test whether the intervention group has lower rates of opioid overdose and longer time to occurrence of overdose. Overdose will be ascertained at 12 months via self-report and across at least 24 months via administrative data. Because randomized controlled studies are designed to account for potential confounding factors by distributing confounders, measured and unmeasured, equally across comparison and intervention groups, the initial unadjusted analysis will be a logistic regression analysis comparing the probability of opioid overdose in the two study arms. To examine differences in the time to overdose and to account for time varying covariates, such as overdose risk factors, survival analyses will be conducted with the outcome time to overdose(s). A Cox proportional hazards model will be used to investigate the possible association between these factors and event time. We will use sandwich standard error estimates in all statistical tests. Multivariable logistic regression analyses will be conducted to examine the association between predictors and moderators and of the odds of overdose occurrence. Predictors will include treatment assignment and overdose risk factors such as concomitant drug use, interruption in tolerance and homelessness. Potential effect modification will be assessed by including interaction terms for the treatment assignment by severity of opioid and other substance use as measured by the ASSIST. For the pharmaceutical opioid only group, effect modification by opioid user type will be assessed; opioid user typologies will be based upon which inclusion criteria subjects met.

Aim 2 Test whether the intervention group has fewer overdose risk behaviors. These are measured as both binary and continuous data. Binary data will be examined with logistic

regression and continuous data analyzed with ordinary least-squares regression. Analyses will adjust for the overdose risk behavior level or frequency reported at baseline as a concomitant variable, the outcome is the overdose risk behavior at 12 months, and the primary predictor is the treatment group assignment. We will compute robust standard error estimates for each model and use them in all hypothesis tests and confidence intervals.

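### The post-hoc crossover comparison classes control subjects by naloxone access during months 0-12 but counts their overdoses from randomisation, so it can show a difference when naloxone has no effect

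*Combined protocol and SAP*

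**What the plan says.** All places are in the combined protocol and SAP.

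- **Primary approach** (Planned methodology): "Intent to treat analyses will be the primary analytic approach".
- **Status of the crossover work** (Other analyses): "Subsequent to intent to treat analyses we will examine whether any subjects in the standard care group received take-home naloxone", together with overdose training. The comparison is made only if such a group exists.
- **Comparison** (Other analyses): "post-hoc analyses will compare overdose rates at two years for the cross over group compared to each of the other two study arms". The crossovers are described as a possible intermediate group, which implies three groups and a standard-care arm without them.
- **Classification** (Other analyses): "Crossovers will be identified by an interview question", for example "Did you possess or have ready access to naloxone during the past 3/6 months".
- **Windows of the question** (footnote to the data schedule): "Past 3 months timeline for 3 and 6 month follow ups, past 6 months used at 12 month follow up". Together these cover months 0-3, 3-6 and 6-12.
- **Naloxone at entry** (Exclusion criteria, item 9) is an exclusion: "Have non-expired take-home naloxone at home, on their person, or in their possessions". Access in the standard-care arm therefore arises after enrolment.
- **Outcome period** (Planned analyses, Aim 1): "Overdose will be ascertained at 12 months via self-report and across at least 24 months via administrative data".

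The comparison carries no stated landmark, exposure date or covariate adjustment.

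**The concern.** Membership of the crossover group is settled by something that happens during the first year, while the outcome is counted from randomisation. A control subject who overdoses in month 1 and obtains naloxone in month 2 enters the crossover group with an overdose that the naloxone could not have prevented. The same overdose leaves the standard-care group, which is then no longer the group formed by randomisation. Both movements widen the gap.

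The plan suggests that crossovers might resemble the intervention arm more than standard care, so the result is likely to be read as information on contamination. A raised rate in crossovers could then be taken as a sign that naloxone outside the study does not help or does harm, when it only reflects the order of events.

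**Working it through.** **Plan's own figure.** The plan gives no figure for the crossover comparison. The event rates come from Sample Size Calculation, whose 219 per arm (20% against 10%, power 0.80, level 0.05) is reproduced exactly with a two-sided test and continuity correction. Without the correction it is 199.

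**Inputs from the documents**
- 250 per arm in each user type.
- Heroin users: 20% overdose per year.
- Pharmaceutical opioid users: 10% per year, 20% over two years.
- Access is asked about only up to month 12, so only year-1 overdoses can lead to crossover status.

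**Assumptions**
- Naloxone has no effect and the two randomised arms have equal risk.
- r1 is the year-1 overdose risk. r2 is the year-2 risk in those free of overdose in year 1, and is unrelated to access.
- Heroin: r1 = 0.20 and r2 = 0.20, so the two-year risk is 0.20 + 0.80 × 0.20 = 36%.
- Pharmaceutical: r1 = 0.10 and r2 = 0.10/0.90 = 0.111, so the two-year risk is 20%.
- q0 and q1 are the chances of year-1 access without and after a year-1 overdose. The documents give neither, so a range is shown.

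**Formulas**
- Share crossing over: pA = r1·q1 + (1 − r1)·q0
- Year-1 overdose among crossovers: a = r1·q1/pA
- Year-1 overdose among remaining controls: b = r1·(1 − q1)/(1 − pA)
- Two-year rates: a + (1 − a)·r2 and b + (1 − b)·r2

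**Heroin, q0 = 10%, q1 = 20%**
- pA = 0.04 + 0.08 = 0.12, or 30 of 250
- a = 0.04/0.12 = 0.333; two-year rate 0.333 + 0.667 × 0.20 = 46.7%
- b = 0.16/0.88 = 0.182; two-year rate 0.182 + 0.818 × 0.20 = 34.5%

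**Pharmaceutical, q0 = 5%, q1 = 30%**
- pA = 0.03 + 0.045 = 0.075, or about 19 of 250
- a = 0.03/0.075 = 0.40; two-year rate 0.40 + 0.60 × 0.111 = 46.7%
- b = 0.07/0.925 = 0.0757; two-year rate 0.0757 + 0.9243 × 0.111 = 17.8%

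| Stratum | q0, q1 | Crossovers | Remaining controls | Intervention arm |
|---|---|---|---|---|
| Heroin | 10%, 10% | 36% | 36% | 36% |
| Heroin | 10%, 20% | 47% | 35% | 36% |
| Heroin | 5%, 30% | 68% | 32% | 36% |
| Pharmaceutical | 10%, 10% | 20% | 20% | 20% |
| Pharmaceutical | 10%, 20% | 27% | 19% | 20% |
| Pharmaceutical | 5%, 30% | 47% | 18% | 20% |

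If the standard-care arm were kept whole, its rate would equal the intervention column. Most of the gap would remain.

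**How often the false difference reaches p<0.05.** Null simulations used 250 per arm, 10% base access, Fisher's exact test against remaining controls and 1,000 runs. The access hazard after overdose was multiplied by a set factor:
- ×1: about 4% in both strata
- ×2: 9% heroin, 6% pharmaceutical
- ×4: 34% and 26%
- ×8: 85% and 66%

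**Check of a 12-month landmark** (heroin, ×4). Counting only year-2 overdoses gives 19.8% against 19.9%, with p<0.05 in 3.7% of runs, when all subjects share one risk. If underlying risk varies (assumed gamma variance of 1), 21.0% against 17.9% remains, with p<0.05 in 6.5%. The landmark removes the order-of-events bias but not confounding by risk.

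**The case against.** The strongest case against is that this matters little. The comparison is conditional, labelled post hoc and placed after the intent-to-treat analysis; no aim or power figure depends on it. That stands and limits the weight of the point. It does not remove the point, because the comparison is written into the plan and can be corrected now.

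Second, the mechanism is assumed. The documents nowhere say that an overdose leads to naloxone supply in standard care, and Intervention Description says standard care would not include the study's package. This also stands: the bias runs down to zero, and a doubled access hazard barely raises the false-positive rate. But the definition does nothing to exclude the mechanism.

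Third, a reader might apply a single 20% overdose risk to the whole two years and let every overdose raise access. That gives 60% against 15.6% (access 30% and 5%: 0.06/0.10 and 0.14/0.90) or 33% against 18% (20% and 10%: 0.04/0.12 and 0.16/0.88). The documents do not support this. Interviews end at 12 months, so year-2 overdoses cannot make anyone a crossover, and 20% over two years is the plan's figure for pharmaceutical users only.

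Fourth, much of the remedy is already available. The data schedule lists overdose dates in the administrative data and days of naloxone possession from interviews. Aim 1 plans a Cox model with time-varying covariates. Naloxone is not named there, however, and the crossover paragraph does not use that model.

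**Conclusion.** The concern holds for the post-hoc crossover comparison only. As written, it can produce a false difference with zero naloxone effect whenever an overdose makes later access more likely. Under the assumed access rates the gap between crossovers and remaining controls is about 8 to 29 percentage points for pharmaceutical users and 12 to 36 for heroin users. It is nil if access is unrelated to overdose.

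Two stronger inferences are not supported. The intent-to-treat result is not compromised, since it keeps every subject in the assigned arm. Nor would this mechanism manufacture a benefit of naloxone: in these scenarios crossovers look worse than both arms. A bias the other way is possible, because subjects who die or are lost before an interview cannot be classed as crossovers, but this was not modelled.

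**What to change.** Replace the three-group two-year comparison in Other analyses with the following.

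- Enter naloxone access as a time-varying exposure in the Cox model already planned for Aim 1, or classify access at a 12-month landmark.
- Count as exposed only overdoses after the interview at which access is first reported.
- Adjust for baseline overdose risk factors and label the result descriptive, because confounding by risk can remain.
- Report the crossover rate alongside the intent-to-treat result.

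Do not add a complier-average estimate based on naloxone access. Assignment also works through counselling and overdose education, so it does not act through naloxone alone.

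The cost is SAP wording; no new data collection is needed. There will be fewer events and less precision. Access time before the reporting interview is counted as unexposed. With the landmark, outcomes after month 12 rest on administrative records alone.
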